11.5.3 Pharmacokinetics

The 15 minute post-dose concentrations in Cohort 3 will be listed by treatment, patient and visit/sampling time point. Descriptive statistics will be provided by treatment and visit/sampling time point. Summary statistics will include mean (arithmetic and geometric), SD, and CV (arithmetic and geometric), median, minimum and maximum. Concentrations below the LLOQ will be treated as zero in summary statistics. A geometric mean will not be reported if the dataset includes zero values.

Corporate Confidential Information

11.6 Sample size calculation

Cohort 1 and 2: The first and second cohort will include 8 patients each, randomized 3:1 to drug: placebo. The sample size of 8 patients per cohort was based on practical considerations and clinical judgment that the numbers of patients are appropriate for the assessment of overall safety and tolerability and for providing adequate confidence for dose escalation. In cohort 1, for instance, an adverse event with an incidence of 23.5% will have a probability of 80% of occurring in at least one patient and a probability of 43% of occurring in two or more patients.

Cohort 3: Based on drop-out rate during the study, up to 40 patients may be randomized to cohort 3 to ensure that at least 24 complete both periods.

^C
Corporate Confidential Information

C

o

11.7 Power for analysis of key secondary variables

Not Applicable

Corporate Confidential Information

12 Ethical considerations

12.1 Regulatory and ethical compliance

This clinical study was designed and shall be implemented and reported in accordance with the ICH Harmonized Tripartite Guidelines for Good Clinical Practice, with applicable local regulations (including European Directive 2001/20/EC, US Code of Federal Regulations Title 21, and Japanese Ministry of Health, Labor, and Welfare), and with the ethical principles laid down in the Declaration of Helsinki.

12.2 Responsibilities of the investigator and IRB/IEC

Before initiating a trial, the investigator/institution should obtain approval/favorable opinion from the Institutional Review Board/Independent Ethics Committee (IRB/IEC) for the trial protocol, written informed consent form, consent form updates, patient recruitment procedures (e.g. advertisements) and any other written information to be provided to patients. Prior to study start, the investigator is required to sign a protocol signature page confirming his/her agreement to conduct the study in accordance with these documents and all of the instructions and procedures found in this protocol and to give access to all relevant data and records to Novartis monitors, auditors, Novartis Quality Assurance representatives, designated agents of Novartis, IRBs/IECs, and regulatory authorities as required. If an inspection of the clinical site is requested by a regulatory authority, the investigator must inform Novartis immediately that this request has been made.

For multi-center trials, a Coordinating Investigator will be selected by Novartis around the time of Last Patient Last Visit to be a reviewer and signatory for the clinical study report.

12.3 Publication of study protocol and results

Novartis assures that the key design elements of this protocol will be posted in a publicly accessible database such as clinicaltrials.gov. In addition, upon study completion and finalization of the study report the results of this trial will be either submitted for publication and/or posted in a publicly accessible database of clinical trial results.

13 Protocol adherence

This protocol defines the study objectives, the study procedures and the data to be collected on study participants. Additional assessments required to ensure safety of patients should be administered as deemed necessary on a case by case basis. Under no circumstances should an investigator collect additional data or conduct any additional procedures for any research related purpose involving any investigational drugs.

Investigators must apply due diligence to avoid protocol deviations. If the investigator feels a protocol deviation would improve the conduct of the study this must be considered a protocol amendment, and unless such an amendment is agreed upon by Novartis and approved by the IRB/IEC/REB/regulatory authority it cannot be implemented. All significant protocol deviations will be recorded and reported in the CSR.

## 1 Introduction

### 1.1 Scope of document

The RAP documents contain detailed information to aid the production of Statistics & Programming input into the Clinical Study Report (CSR) for trial “CQBW276X2201”.

The Statistical analysis plan (SAP) describes the implementation of the statistical analysis planned in the protocol.

### 1.2 Study reference documentation

This SAP has been developed using Clinical Trial Protocol version v02 dated 20-Mar-2017.

### 1.3 Study objectives

#### 1.3.1 Primary objectives

Primary Objective: Cohort 1 and 2	Endpoints

To assess the safety, tolerability and PK of multiple doses of inhaled QBW276 and its metabolites over 1 or 2 weeks of treatment in patients with CF

	

All safety assessments during the cohort period, including:

Physical examination

Hematology

Blood chemistry (central and local labs)

Urinalysis

ECG evaluation

Vital Signs

AEs and SAEs

PK measurements

Primary Objective: Cohort 3	Endpoints

To evaluate the response to multiple doses of inhaled QBW276 in lung function (percent of predicted FEV1) over 4 weeks of treatment compared with placebo in patients with CF that are homozygous for the F508del mutation.

	

% predicted FEV1 (assessed by spirometry)

### **1.3.2 Secondary objectives**

#### **Secondary Objective: Cohort 1 and 2**

- To evaluate the response to multiple doses of inhaled QBW276 on change in lung function (percent of predicted FEV1 and LCI) in patients with CF

#### **Endpoints**

- % predicted FEV1 (assessed by spirometry)
- LCI2.5 (assessed by Multiple Breath Nitrogen Washout [MBNW]) if FEV1 at screening is > 80% of predicted

#### **Secondary Objective: Cohort 3**

- To assess the safety, tolerability, PK and of multiple doses of inhaled QBW276 and its metabolites over 4 weeks of treatment in patients with CF who are homozygous for the F508del mutation

#### **Endpoints**

- All safety assessments during the cohort period, including:
  - Physical examination
  - Hematology
  - Blood chemistry
  - Urinalysis
  - ECG evaluation
  - Vital Signs
  - AEs and SAEs
- LCI2.5 (assessed by MBNW) if FEV1 at screening is > 80% of predicted
- PK measurements

[figure not shown]
Corporate Confidential Information

## Corporate Confidential Information

## 1.4 Study design and treatment

This is a study of multiple doses of inhaled QBW276 in patients with CF on top of Standard of Care, Corporate Confidential Information CFTF potentiators and correctors, if applicable. The study will be divided into three cohorts. Cohorts 1 and 2 are designed to be a randomized, double-blind, placebo-controlled, parallel arm multiple ascending dose study of the safety, tolerability, PK and preliminary efficacy of inhaled QBW276 over 1 week (cohort 1) and 2 weeks (cohort 2) in patients with CF regardless of their genotype. The primary rationale for cohorts 1 and 2 will be to assess PK, safety and tolerability in CF. Cohort 3 is a randomized, double-blind, placebo-controlled, cross-over design multiple dose study of the efficacy, safety, tolerability, and PK of inhaled QBW276 over 4 weeks in patients with CF who are homozygous for the F508del mutation. Corporate Confidential Information

**Figure 1-1** Schematic for study design

Cohort 1 will receive 3 mg bid dose (6 mg/day) or placebo over 1 week. Corporate Confidential Information

Upward, downward, or repeat dosing will continue in cohorts 2 and 3, as long as the systemic exposure cap based on pre-clinical data or a clinical maximum tolerated dose (MTD) is not exceeded. Cohorts 1 and 2 will enroll 8 patients each, with 6 patients randomized to receive active drug and 2 patients randomized to receive matching placebo. Cohort 1 will be dosed for 1 week while cohort 2 will be dosed for 2 weeks. Cohort 2 will be initiated only after cohort 1 has completed dosing. Cohort 2 may be skipped if safety, tolerability, PK data from cohort 1 are found favorable to proceed directly to cohort 3. In cohorts 1 and 2, patients may be replaced if they do not complete the study duration for reasons other than safety to obtain 8 completers in each cohort. If a patient has participated in cohort 1, he/she may qualify to participate in cohort 2 contingent upon approval from the sponsor, as long as he/she has been through a 4 week wash-out between dosing in the two cohorts, and has not experienced any significant AEs since enrollment in cohort 1. This will ensure that no patient receives more than 4 weeks of the investigational drug QBW276 in his/her lifetime until further supportive toxicology studies are conducted in the drug's development program.

NOTE: No patient randomized to cohort 1 or 2 will be eligible for cohort 3.

### **Cohort 1 and 2**

Cohorts 1 and 2 will consist of a 21 day screening period followed by a baseline visit and a 7 or 14 day Treatment Period in cohort 1 and 2, respectively. Adequate windows will be provided for patient's convenience. QBW276 will be administered on top of the patient's usual standard of care medications.

Study inclusion/exclusion criteria as well as medication use will be assessed at screening. Patients who meet the inclusion/exclusion criteria at screening will report to the study site on Day -1 at a time specified by the investigator, for the baseline assessments. All baseline safety evaluation results must be available prior to dosing on Day 1, hence, Day -1 assessments can be carried out up to 72 hours prior to Day 1 dosing.

Patients who meet all of the inclusion and none of the exclusion criteria at baseline will then report to the study site on Day 1 and will remain in the clinic until at least 6 hours after the first dose in the morning.

On Day 1, pre-dose safety, biomarker, PK blood draw, and urine collection will be performed. Following the pre-dose procedures, subjects will be randomized. Post-dose evaluations will include routine safety evaluations and blood for PK assessments. The patients will be asked to return to the study site for follow-up visits as specified on the respective assessment schedules.

[figure not shown]
Safety will be monitored by assessment of vital signs, physical examination, ECG, clinical laboratory evaluations (hematology, blood chemistry, and urinalysis), urine electrolytes, aldosterone in plasma, lung function, and monitoring of adverse events (AEs) throughout the study. PK (drug and metabolites) Corporate Confidential Information

measured in cohorts 1 and 2 will be compared with data from the healthy volunteer study.

A blinded review of data will be conducted after completion of each cohort prior to initiation of the next cohort. The Sponsor (medically qualified representative) in conjunction with the designated site Investigator(s) will review blinded data (including lung function, AEs, vital signs, safety laboratory parameters including aldosterone values, and PK). An external data monitoring committee (DMC) will also be assembled to monitor study safety data as per an approved charter. After the first 4 patients in Cohort 1 have completed the Day 7 study assessments, the PK data may be reviewed by the study pharmacokineticist to compare exposure levels with previously observed data in healthy patients.

### **Cohort 3**

Dosing in cohort 3 will not commence until the Sponsor (medically qualified representative) in conjunction with the designated site Investigator(s) have reviewed all available safety, tolerability, PK, data from cohorts 1 and/or 2. Endorsement for the dose selected for cohort 3 will also be sought from the DMC members per the DMC charter.

**Figure 1-2** Schematic for Cohort 3 study design

\*For patients on inhaled antibiotics, the study drug will be started on the 7th day (+/- 2 days) of inhaled antibiotic use during their 28 day antibiotic cycle.

For Cohort 3, patients will be randomized to one of two treatment sequences: QBW276 in Period 1 and Placebo in Period 2 or Placebo in Period 1 and QBW276 in Period 2. Based on drop-out rates observed during conduct of the study, up to 40 patients will be randomized to ensure that at least 24 patients complete the study. After a 4 week screening period, patients who meet all selection criteria will receive drug for 4 weeks and placebo for 4 weeks, separated by a 4 week wash out period, or vice versa. QBW276 will be administered on top of the patient's usual standard of care medications. Periods 1 and 2 will commence on day 7 (+/- 2) of the patient's standard of care cyclic inhaled antibiotic regimen.

Screening and baseline visits for cohort 3 will be similar to the respective visits in cohorts 1 and 2. On Day 1 of cohort 3, pre-dose safety, efficacy and biomarker collection will be performed. Following the pre-dose procedures eligible patients will be dosed for up to 28 days. Post-dose evaluations will include routine safety evaluations and blood for PK assessments. The patients will be asked to return to the study site for follow-up visits on Days 7, 14, 21, and 28 after which they will undergo a 4 week wash-out period prior to cross-over to the opposite arm, and follow a similar visit schedule until End of Study assessment approximately 7 days after the last visit in the second period. All patients will undergo the same assessments regardless of their dose.

Efficacy will be evaluated by spirometry, multiple breath nitrogen washout (if FEV1 at screening is > 80% of predicted), lung volume measurements, and responses to the CFQ-R. Safety will be monitored by assessment of vital signs, physical examination, ECG, clinical laboratory evaluations (hematology, blood chemistry, and urinalysis), urine electrolytes, aldosterone in plasma, and monitoring of adverse events (AEs) throughout the study.

Randomization will be stratified by Corporate Confidential Information concomitant medication in Cohort 3 only. This is because improvement in lung function after treatment with QBW276 may or may not be synergistic Corporate Confidential Information based on their mechanism of action, Corporate Confidential Information

If a maximum tolerated dose for patients with CF (MTD) is identified in cohorts 1 or 2 on the basis of dose-limiting toxicity, the predicted exposure at the maximum planned dose in cohort 3 shall not exceed the exposure at the MTD. If an MTD is not defined in cohorts 1 and 2, the

maximum planned dose in cohort 3 shall not exceed the systemic exposure cap based on pre-clinical data.

## **2 First interpretable results (FIR)**

First interpretable results (FIR) will be provided for this trial.  
Corporate Confidential Information

Corporate Confidential Information

## **4 Statistical methods: Analysis sets**

For all analysis sets, subjects will be analyzed according to the study treatment(s) received.

The safety analysis set will include all subjects that received any study drug.

The PK analysis set will include all subjects with at least one available valid (i.e. not flagged for exclusion) PK concentration measurement, who received any study drug and experienced no protocol deviations with relevant impact on PK data.

Corporate Confidential Information

The analysis sets and protocol deviation codes are related as follows:

**Table 4-1 Protocol deviation codes and analysis sets**

Category Deviation code	Text description of deviation	Data exclusion
Subjects are excluded from PK analysis in case of these PDs:		Exclude subject from PK analysis set
Subjects are excluded from PD analysis in case of these PDs:		Exclude subject from PD analysis set
Subjects are excluded from PK and PD analysis in case of these PDs:		Exclude subject from PK and PD analysis sets

If updates to this table are needed, an amendment to the SAP needs to be implemented prior to DBL.

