### 6.1.3 Statistical model, assumptions and hypotheses

Percent of predicted FEV1 values measured on Day 7, Day 14, Day 21 and Day 28 of each treatment period at the study site for cohort 3 will be analyzed using a mixed effects model for repeated measurements. The model will include fixed effects for period, time (Days 7, 14, 21, 28 as appropriate), treatment and treatment by time. Subject will be included as a random effect and time will be repeated within each patient by period interaction term. Subject-average baseline and period-adjusted baseline will be fitted as covariates. An unstructured covariance matrix will be applied. In case of the analysis fails to converge, compound symmetric covariance structure will be used in the first instance and if further alterations to the model are necessary the significance of the covariates will be explored. Kenward Roger options will be used to calculate the degrees of freedom in all Proc Mixed analysis.

The subject average baseline will be derived as the average of their pre-dose assessments from each period. Period adjusted baseline will be calculated for each subject and for each period, as the difference between the period baseline and the subject average baseline, i.e. value of period baseline - value of average baseline.

The final model estimates will include the LSmean for each treatment together with standard error (SE), the adjusted mean difference between treatments, and 80% two-sided confidence intervals and P-value for the differences. These will be calculated at all time points, and specifically at the primary time point of interest (Day 28) using Placebo as the reference treatment.

No adjustments for multiplicity will be applied for this exploratory study. Missing data is assumed to be Missing At Random (MAR).

Additional summaries of frequencies of responder rates will be presented. A subject will be considered a responder where improvements are seen such that  $FEV1 > 5\%$  or  $LCI > 1$  unit.

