#### 6.1.3.1 Model checking procedures

The repeated measures analysis includes all available information in terms of measurements at all times. If missing measurements are missing at random, an analysis of the available data provides consistent estimates of model parameters. Reasons for dropouts will be explored.

Where data has values below and above limits of quantification then the following rule will apply.

In the summary tables, the frequency (n, %) of values below the LLOQ and above the ULOQ, respectively, will be included.

Any values below the limit of quantification will be analyzed as 0.5\*the lower limit, both in the descriptive and the model analysis. Any values above the limit of quantification will be analyzed as 1.0\*the upper limit, both in the descriptive and the model analysis.

No other imputation of missing data is allowed.

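### SAP Table 4-1 shows only whole-subject exclusion; in the Cohort 3 cross-over, a listed deviation confined to one visit or period would discard up to 7 or about 4 usable FEV1 values.

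*SAP*

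**What the plan says.** SAP Table 4-1 has three rows of deviations: those affecting PK, PD, or both. The PD row is introduced by "Subjects are excluded from PD analysis in case of these PDs" and its action is "Exclude subject from PD analysis set"; the other two rows act on the subject in the same way. The deviation codes and descriptions are not readable in the public text, and the passage where the PD analysis set would be defined is blacked out in both documents. Below the table the SAP adds: "If updates to this table are needed, an amendment to the SAP needs to be implemented prior to DBL".

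Cohort 3 randomises patients to "QBW276 in Period 1 and Placebo in Period 2 or Placebo in Period 1 and QBW276 in Period 2". The primary model in SAP 6.1.3 uses "Percent of predicted FEV1 values measured on Day 7, Day 14, Day 21 and Day 28 of each treatment period" and reports "80% two-sided confidence intervals and P-value for the differences". SAP 6.1.3.1 (and Protocol 11.4.3) says of the model: "The repeated measures analysis includes all available information in terms of measurements at all times". Missing data are assumed missing at random.

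For PK, Protocol 11.1 and SAP section 4 already work at a finer level as well: the set definition refers to concentrations that are valid because they have not been flagged for exclusion. No equivalent flag for FEV1 is visible.

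**The concern.** A repeated-measures model in a cross-over does not need complete subjects. If one reading or one period is compromised, the remaining values still carry information on the treatment contrast. An exclusion rule whose only unit is the subject gives that information away.

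Localised deviations are foreseeable here. Protocol 6.9 lets a visit go ahead after bronchodilator use in the restricted window, with the use recorded; that may distort one reading. Protocol 7.1 lists use of prohibited treatment and a threshold of missed doses as reasons to stop study treatment; in Period 2, either leaves Period 1 and the earlier Period 2 visits intact.

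Two things are at stake. The first is precision, in a cohort sized for 24 completers. The second is selection: such events occur after randomisation and may depend on the treatment being taken. Removing the subject also removes the outcomes recorded before the event and all data on the other treatment, which are the data that would make the missing-at-random assumption more plausible.

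**Working it through.** **The plan's own figure.** The documents give no count of FEV1 values lost per exclusion, and the Cohort 3 effect size, SD and power are blacked out, so there is no figure of this kind to reproduce. Protocol 11.6 gives only the size: "up to 40 patients may be randomized to cohort 3 to ensure that at least 24 complete both periods". The implied allowance for non-completion is 1 − 24/40 = 40%.

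**Step 1: values lost.** Four modelled visits (Days 7, 14, 21, 28) × 2 periods = 8 values per completer.
- One bad visit: 8 − 1 = 7 valid values discarded.
- One whole bad period: 8 − 4 = 4 valid values discarded. If the deviation starts partway through the period, the number is higher; for example, onset after Day 14 spoils 2 values, so 8 − 2 = 6 valid values go.

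Eight is the total removed, affected values included.

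**Step 2: simple precision check.** Excluding k of 24 subjects multiplies the SE by √(24/(24 − k)):
- k = 1: 1.022
- k = 2: 1.044
- k = 3: 1.069
- k = 4: 1.095

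For k = 3 the 80% half-width, using a normal quantile and in units of the SD of the within-patient difference, goes from 0.262 to 0.280.

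With 12 subjects per sequence, losing 2 from one and 1 from the other gives √[(1/10 + 1/11)/(1/12 + 1/12)] = √(0.1909/0.1667) = 1.070, the 7.0% seen below.

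**Step 3: generalised least squares for the Day 28 contrast.** Fixed effects: four visit means, one period effect, and a treatment effect at each visit. Unit variance, known covariance, no baseline covariates. One correlation applies within a period and another across periods; both are assumptions, since the documents give none. SE of the Day 28 effect = square root of its diagonal element in (ΣXᵢ′Vᵢ⁻¹Xᵢ)⁻¹. Three of 24 subjects are affected; the entries are SE increases over full data.

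| Within / across correlation | Whole subject out | Period 2 out | One Day 28 visit out | One Day 14 visit out |
|---|---|---|---|---|
| 0.67 / 0.2 | 7.0% | 4.0% | 1.8% | 0.0% |
| 0.80 / 0.7 | 7.0% | 4.8% | 2.8% | 0.0% |
| 0.90 / 0.8 | 7.0% | 5.3% | 2.1% | 0.0% |
| 0.95 / 0.9 | 7.0% | 5.5% | 2.2% | 0.0% |

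The ranges quoted in this point are those of these four pairs. The Day 28 column is the most sensitive to the pairing: rerunning the same calculation at 0.95/0.2 gives 0.3% and at 0.67/0.6 gives 3.3%.

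The avoidable part is therefore 7.0 − 5.5 = 1.5 to 7.0 − 4.0 = 3.0 points for a period-confined deviation, 7.0 − 2.8 = 4.2 to 7.0 − 1.8 = 5.2 points for a Day 28 visit, and essentially all 7 points for a Day 14 visit.

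**Step 4: discontinuation in Period 2.** Such a patient is not a completer and comes on top of the 24. Adding three patients with Period 1 data only to 24 completers lowers the Day 28 SE by 1.2–2.4% over the same four pairs. That, not 7%, is what whole-subject exclusion forgoes in this case.

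**The case against.** The strongest objection is that the trigger cannot be seen. A reader might infer that one bad visit or one prohibited medicine does remove the patient. The documents do not show this: the codes are unreadable, and all of them may be deviations that invalidate the whole subject, such as not being homozygous for F508del, for which whole-subject exclusion is reasonable. Nor can the unreadable cells be counted as an omission, or a measurement-level flag be ruled out in the blacked-out PD definition. This stands, and it makes the harm conditional.

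A reader might also conclude that the plan biases the primary estimate by removing patients who did badly on one treatment. That needs a listed code tied to a post-randomisation event, and none is visible. Stopping treatment under Protocol 7.1 is a separate matter: the resulting missing visits are handled by the model under missing at random, not by Table 4-1. Selection is a possibility, not a finding.

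Third, the loss is modest and the study is non-confirmatory, with 80% intervals and no multiplicity control. That is fair on priority. The number of affected subjects, 3, is also an illustration without a source in the documents.

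Fourth, changes to the table already require an amendment before database lock. That controls when the rule can change, not the unit of exclusion.

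What remains is that the readable action is at subject level, the model can use partial data, and a finer rule costs almost nothing.

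**Conclusion.** The point holds in conditional form. Every readable action in Table 4-1 excludes the whole subject, which fits poorly with a cross-over model built to use all available measurements. If any listed deviation is confined to a visit or a period, up to 7 or about 4 otherwise valid FEV1 values per patient are lost, and patients could be selected on what happened after randomisation. To say that eight valid values are lost to one bad visit or period would overcount, since eight includes the affected ones.

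The precision cost is about 2% in SE for one excluded subject out of 24 and about 7% for three. How much of it is avoidable depends on how local the deviation is: least for a whole period, nearly all for an intermediate visit. The figures rest on the assumed correlations, a known covariance and no baseline covariates. This is a cheap improvement, not a defect that undermines the primary analysis.

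**What to change.** Use the amendment route stated under Table 4-1. For Cohort 3, reword the PD action along these lines: exclude the affected assessments (visit or period); the subject stays in the PD analysis set unless the deviation invalidates both periods. Fix the list of affected assessments on blinded data before database lock.

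Say also what happens when the affected assessment is a period's baseline spirometry, because the subject-average baseline in SAP 6.1.3 draws on both periods.

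For PK, use the existing measurement-level flag in place of subject exclusion when a deviation affects only some samples.

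If every listed code already invalidates the whole subject, one sentence saying so is enough. Otherwise the cost is a visit-level flag in the analysis dataset and slightly more work at the blinded deviation review.
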